## 2.5 Risk-Benefit Assessment

The presently proposed Phase II study (MIV-711-202) is the third clinical study with MIV-711 and as such it has the potential to determine the 12 month safety of MIV-711 in treating painful, radiographic knee OA, as well as the effect over 6 months in patients with progressing symptomatology.

The toxicity of MIV-711 has been studied in mouse and monkey up to 6 months. In the mouse 6 month study, MIV-711 was well tolerated to systemic exposures of 58  $\mu\text{M} \times \text{h}$  (mean) in terms of  $\text{AUC}_{0-t}$  with no treatment-related microscopic findings. In the 6-month cynomolgus monkey study, the majority of the observed findings were related to MIV-711 pharmacology and the systemic exposure at the no observed adverse effect level (NOAEL) was 15  $\mu\text{M} \times \text{h}$  (mean) in terms of  $\text{AUC}_{0-24}$ . Further data is provided in the IB.

The single dose ranges 20-600 mg and multiple dose ranges 50-200 mg of MIV-711 given q.d. for 7 days have been explored in healthy volunteers. In addition, the 100 mg dose was administered q.d. in a 28-day open care cohort consisting of healthy post-menopausal female volunteers. In these settings, MIV-711 showed acceptable safety and tolerability in conjunction with no clinically significant changes in haematology, clinical chemistry, vital signs or ECG parameters. The study of 200 mg MIV-711 q.d. in man, which constitutes the highest dose in Study MIV-711-201 as well as the only dose administered in Study MIV-711-202 resulted in a 2.4  $\mu\text{M} \times \text{h}$  average  $\text{AUC}_{0-24}$  which corresponds to an expected 6 times margin to the NOAEL level in the cynomolgus monkey.

MIV-711 has consistently shown biomarker effects in the Phase I study that correlates strongly with efficacy on joint structure in the pre-clinical models. The doses of MIV-711 used in Study MIV-711-201 were estimated to provide an exposure sufficient to produce an improvement in joint structure and symptoms, as has been shown for other bone-acting agents (see Section 2.1). There is further potential symptom and structure improvement benefit for patients in Study Population A in the present study as the treatment length is extended to a total of 52 (26+26) weeks on 200 mg q.d. MIV-711. This potentially allows measurable changes in cartilage to occur. Furthermore, patients in Study Population B are selected based on clinically significant symptom progression and may therefore benefit more from a potential DMOAD compared to stable patients. The potential for benefit together with the hitherto favourable safety and toxicology profile converge into a favourable Benefit/Risk assessment for the present study.

No safety-related trends have been identified in the ongoing Study MIV-711-201 and it is believed that MIV-711 has acceptable safety and tolerability in OA patients based on the blinded results so far. By the start of enrolment into the present study, at least one Data Monitoring and Ethics Committee (DMEC) meeting reviewing the safety data of

Study MIV-711-201 will have been finalized. For the present study, the DMEC will reconvene to review the unblinded safety and tolerability data after the first 25 patients complete Visit 4 and Visit 5.

With regard to previous clinical experience (see IB for further information), there are at present time no approved cathepsin K inhibitors on the market, although several have been/are in clinical stages of development. The clinical data on these other compounds are only available in part from meeting abstracts and published progress reports. However it is judged that there is no indication of any class effect, or otherwise collectively significant findings in the available data that would infer any added risk to the Benefit/Risk assessment for the present study.

On the basis of the pre-clinical and clinical data on MIV-711 to date and the favourable Benefit/Risk balance, it is considered appropriate to proceed with the Phase II extension study which is proposed in the present protocol.

### 3 STUDY OBJECTIVES

#### 3.1 Primary Objective Study Population A\*

To assess the safety and tolerability of 200 mg MIV-711 q.d. over 52 (26+26) weeks in patients with symptomatic and radiographic knee osteoarthritis.

\* Study Population A will be recruited from patients treated with 200 mg MIV-711 q.d. in Study MIV-711-201 and whose symptoms did not clinically significantly deteriorate as defined by an increase in NRS of  $\leq 2$  compared to Baseline.

#### 3.2 Secondary Objectives Study Population A

To assess, in patients with symptomatic and radiographic knee OA, over 52 (26+26) weeks:

- The effect of MIV-711 on MRI cartilage thickness loss
- The effect of MIV-711 on MRI bone marrow lesion volume
- The effect of MIV-711 in the semi quantitative MRI Osteoarthritis Knee Score (MOAKS) parameters
- To assess the effect of MIV-711 on MRI knee joint bone area.

Note: all MRI assessments refer to the target knee unless stated otherwise.

Target knee is identified by knee pain on a numeric rating scale and Kellgren and Lawrence classification grade. If patients have knee pain in both sides with equal regard to these two criteria, the right knee should always be prioritized. The target knee in Study MIV-711-202 must be the same as in Study MIV-711-201.

#### 3.3 Secondary Objective Study Population B\*

To assess the effect of 200 mg MIV-711 q.d. on safety and tolerability over 26 weeks in patients with symptomatic and radiographic knee osteoarthritis.

\* Study Population B will be recruited from patients receiving placebo in Study MIV-711-201 having experienced a clinical worsening as defined by an increase in NRS of  $\geq 2$  versus Baseline.

#### 3.4 Exploratory Objectives Study Population A

In addition, the study will address the following exploratory parameters:

- The effect of MIV-711 on worst target knee pain (1 week recall)
- The effect of MIV-711 on average contralateral knee pain (1 week recall)
- The effect of MIV-711 on constant and intermittent OA pain
- The effect of MIV-711 on global improvements in knee problem, knee pain and knee function
- The effect of MIV-711 on knee joint OA symptoms (function, pain, stiffness)
- The effect of MIV-711 on global disease activity
- The effect of MIV-711 on quality of life (QoL)
- The effect of MIV-711 on patient reported e-diary daily recall knee joint pain
- The effect of MIV-711 on patient reported e-diary daily recall analgesics use
- Assessment of the effect of MIV-711 on exploratory serum and urinary biomarkers of relevance for OA including but not limited to procollagen type I N-terminal propeptide (PINP), bone specific alkaline phosphatase (BSAP), N-terminal telopeptide of collagen type I (NTX-I), CTX-I,  $\alpha$ CTX-I, CTX-II and tartrate-resistant acid phosphatases (TRAP5b).
- Baseline and steady state treatment blood and urinary samples will be stored for patients who sign a separate voluntary Informed Consent Form (ICF) for potential

future pharmacogenomics and disease-related proteomics, genomics, metabolomics and lipidomics analyses.

- The effect of MIV-711 on a compound index of MRI bone area and cartilage thickness
- The pharmacokinetics of MIV-711 and the relationship to patient factors and concomitant medications

### **3.5 Exploratory Objectives Study Population B**

[figure not shown]
All of the above denoted secondary and exploratory parameters described in Section 3.2 and Section 3.4 for Study Population A, are considered as exploratory objectives in Study Population B and will be evaluated over 26 weeks.

#### 4 OVERALL DESIGN AND PLAN OF THE STUDY

This is a multicentre, open-label, one-arm Phase II extension study to evaluate the safety and tolerability of MIV-711 in patients with knee joint OA.

The clinical study, which involves the use of an IMP, has been designed and will be run in accordance with the principles of Good Clinical Practice (GCP) and the current regulatory requirements as detailed in the Clinical Trial Directive 2001/20EC and any subsequent amendments of the clinical study regulations.

All patients in Study MIV-711-201 (Eudract No. 2015-003230-26) at the participating sites included in Study MIV-711-202 will be given the opportunity to participate provided that they meet the eligibility criteria. The transition from Study MIV-711-201 to MIV-711-202 is shown in Figure 1.

**Figure 1: Transition from Study MIV-711-201 to Study MIV-711-202**

To ensure the patients will have sufficient time to consider their participation in the study the informed consent form will be given to the patients prior to Visit 8 in Study MIV-711-201. Visit 8 of Study MIV-711-201 will ideally be conducted on the same day as Visit 1 of the present study. If these visits are conducted on the same day the results of the following assessments will be recorded in the electronic Case Report Form (eCRF) for both studies; urine and blood sampling for safety, vital signs, physical examination and ECG. See Section 8.1.1 for a full list of assessments required at Visit 1.

A central person, independent from the study, with access to the randomisation list and the eCRF for Study MIV-711-201 study will confirm Inclusion Criterion 1. The confirmation will be communicated to the site staff and the study team via fax/email without revealing the treatment in MIV-711-201 or the change in NRS score.

All enrolled patients will receive 200 mg q.d. oral dose of MIV-711 for 26 weeks in addition to their current medication. MIV-711 200 mg will be provided as identical capsules to those used in Study MIV-711-201.

The patients will take the last dose of IMP in Study MIV-201-711 at Visit 8 and dosing in the present study will be started at Visit 2 after a screening period of 10±5 days. Patients who are

[figure not shown]
not eligible to participate in the present study will return for the safety follow up visit (Visit 9) in Study MIV-711-201.

Patients will be permitted to remain on their current analgesic regimen with any changes in concomitant medications reported and recorded at study visits as well as in a patient reported daily e-diary for two 2-week periods prior to Visit 4 and Visit 5.

The study consists of a Screening period of approximately 2 weeks (Visit 1), eligibility at Visit 2, an open-label treatment period of 26 weeks from Visit 2 through Visit 5, and a follow-up period of 4 weeks (Visit 6) after the last dose of study treatment is administered. Telephone calls will be made 5-9 days after all dosing visits for safety and tolerability. There will be additional phone calls at Week 10 and Week 20 for safety and tolerability.

A DMEC will meet to review the unblinded safety and tolerability data after the first 25 patients complete Visit 4 and Visit 5.

The study design is summarised in Figure 2.

\*) Patients eligible for the MIV-711-202 study will not do the follow up visit in the MIV-711-201 study but the corresponding visit in the MIV-711-202 study.

**Figure 2: Study Design**

## 5 STUDY POPULATION

The study population will consist of patients with symptomatic and radiographic knee joint OA who have participated in Study MIV-711-201. Patients must be able to provide written consent and meet all the inclusion criteria and none of the exclusion criteria.

### 5.1 Inclusion Criteria

Patients must meet all of the following criteria to be eligible for enrolment in this study:

1. Previously enrolled in Study MIV-711-201 including completion of Visit 8 either by
  - Receiving MIV-711 200 mg and had non-significant clinical worsening on the primary endpoint as defined by NRS increase of  $\leq 2$

OR by

- Receiving placebo and had a clinically significant worsening on the primary endpoint as defined by NRS increase of  $\geq 2$

The NRS result will be derived using the primary endpoint from Study MIV-711-201: NRS average knee pain in the target knee with 7 days recall: increase from Baseline (Visit 2 of Study MIV-711-201) to Visit 8 of Study MIV-711-201.

2. Female patients must be non-pregnant, non-lactating and of non-childbearing potential either as naturally (spontaneously) post-menopausal or due to hysterectomy and/or bilateral oophorectomy/salpingo-oophorectomy (as determined by patient medical history). Naturally (spontaneously) post-menopausal is defined as being amenorrhoeic for 12 months without an alternative medical cause and with a Screening follicle stimulating hormone test indicating post-menopausal state.
3. Male patients should avoid fathering a child by either of the following methods:
  - True sexual abstinence: meaning that heterosexual abstinence is in line with the preferred and usual lifestyle of the patient (periodic abstinence such as that based on calendar, ovulation, symptothermal, post-ovulation methods, declaration of abstinence for the duration of a trial, or withdrawal/coitus interruptus are not acceptable methods of contraception).
  - Willingness to use two effective means of contraception with their partner from the time of first IMP administration until 3 months after the last dose of IMP. Two or more of the following methods are acceptable and must include at least one barrier method: i) Surgical sterilisation (i.e., bilateral tubal ligation for female partners; vasectomy for male), ii) placement of an intrauterine device or intrauterine system, iii) hormonal contraception (implantable, patch, oral), iv) barrier methods including condom or occlusive cap (diaphragm or cervical/vault caps) with spermicidal foam/gel/film/cream/suppository. Male patients who have been sterilised are required to use one barrier method of contraception (condom).
4. The patient's usual analgesic regimen (in case of use) should remain the same as for Visit 8 in Study MIV-711-201 (i.e., Visit 1 in Study MIV-711-202).

NOTE: If a patient is experiencing increased or decreased pain and requires an increase or a decrease in the dose of analgesics, or an occasional change of analgesics medication during his/her participation in the study, then this will be allowed and should be properly documented in the patient file and the CRF.

5. Needs to be able to communicate well with the investigators and staff.

6. Able to comply with the requirements of the study procedures and provide written informed consent prior to any study related procedures.

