#### *9.5.3.1 Definition of Baseline for Exploratory Endpoints*

For the efficacy parameters, for Study Population A, changes from Baseline will be assessed using the Visit 2 baseline data from MIV-711-201. For Study Population B, changes from Baseline will be assessed using the Visit 8 data from Study MIV-711-201 which is expected to occur on the same calendar day as Visit 1 in Study MIV-711-202. For the biomarkers in Study Population B, the baseline will be Visit 2 in the present study (MIV-711-202).

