7.9 Dose Administration

Information collected per the dose administration CRF will be listed including patient number, visit, date and time of administration, number of capsules dispensed and number of capsules returned.

The number and percentage of patients who received IMP will be summarized for each on site visit. Descriptive statistics will be used to summarize drug accountability as the number of capsules returned for each on site study visit by treatment.

Compliance will be derived as the number of days patient were exposed to IMP. 100% compliance will be considered for dosing during the period Visit 2 to Visit 5. The number of capsules used will be derived as the number of capsules dispensed minus the number of capsules returned. Subjects with less than 100% compliance will be identified among those who have results for “Reason not all unused Capsules returned”. The compliance will not be calculated for withdrawn patients, as the date of the last IMP dose taken is not captured in the database.

8. Pharmacodynamic Analysis – Efficacy

The baseline will be the last valid assessment prior to first dose of 200 mg MIV-711, i.e. the baseline visit is defined as

- Visit 2 in study MIV-711-201 for study group A
- Visit 8 in study MIV-711-201 for study group B

The exception is for the biomarkers in study group B, where the baseline visit is defined as visit 2 in the present study (MIV-711-202).

The change from baseline for visit X will be calculated as the (visit X – baseline visit) difference in observed values. Note that the change from baseline will be calculated for all visits in study MIV-711-201 and study MIV-711-202 where the actual endpoint has

PAREXEL International Statistical Analysis Plan

Medivir
Protocol: MIV-711-202

Final 1.0
16 January 2018

been observed, i.e. not only for visits in study MIV-711-202 succeeding the baseline visit.

All efficacy analyses will be made on the ITT population if not stated otherwise.

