8.1.1 Statistical Analysis – Imorphics MRI Assessments

A linear mixed effects model will be used to assess the behaviour of the MRI response over the entire period of the two studies, i.e. from visit 2 in study MIV-711-201 to visit 5 in study MIV-711-202. The model will include fixed factors for study group (A or B), visit, group*visit interaction, baseline analgesic user (Yes/No), and random effect for site and patient.

Patients considered analgesic users at baseline will be identified via concomitant medication analgesic usage. A patient exposed to a prescribed analgesic and ongoing medication at time of the first 200 mg MIV-711 intake (visit 2 study MIV-711-201 for patients in group A and visit 2 study MIV-711-202 for group B) will be considered as a baseline analgesic user.

The dependent variable in the linear mixed model is the observed MRI score. Separate mixed model analyses will be considered for each of the MRI endpoints noted in section 8.1. The following SAS code will be used as default, but a reduced model may be used in case of convergence issues:

```
PROC MIXED data=;  
  CLASS patient visit group baseline_conmed_pain_use;
```

PAREXEL International Statistical Analysis Plan

Medivir
Protocol: MIV-711-202

Final 1.0
16 January 2018

```
MODEL MRI_score = group visit group*visit baseline_conmed_pain_use/ DDFM=KR ;  
RANDOM site;  
REPEATED visit / SUBJECT=patient TYPE=UN;  
LSMEAN group*visit / diff CL ALPHA=0.1 ;  
RUN;
```

In case of convergence issues, a reduced model will be used to achieve convergence. The first two model reductions that will be considered are the following:

1. Simplify the covariance structure by using a compound symmetry covariance structure instead of unstructured.
2. Omit the random effect of site

The mean level and the change from visit 2 in study MIV-711-201 will be estimated for each population*visit combination in the model above together with the corresponding 90% confidence interval. The estimates and confidence intervals will be tabulated and visualized over visits with the two groups in the same table/figure (see example figures and example table below). In this example table and example figures (Figure 1, Figure 2 and Table 1), 'Population A' and 'Population B' refer to Group A and Group B.

PAREXEL International Statistical Analysis Plan

Medivir
Protocol: MIV-711-202

Final 1.0
16 January 2018

Figure 1 Example figure of estimated mean levels

[figure not shown]
[figure not shown]

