8.3.1.1 Statistical Analysis of the NRS Pain Data

The statistical analysis of NRS Pain data will be performed using the same statistical analysis as for the Imorphics MRI described in in section 8.1.1. The output of the statistical analysis will be similar (see example figures and table section 8.1.1.) but will be based on the visits when the NRS assessments were conducted.

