DAY 1	Median	xx.x		xx.x	xx.x
	Min	xx		xx	xx
	Max	xx		xx	xx
	n	nn	nn	nn	nn
VISIT 5	Mean	xx.x	xx.x	xx.x	xx.x
MIV-711-201	SD	xx.xx	xx.xx	xx.xx	xx.xx
WEEK 8	Median	xx.x	xx.x	xx.x	xx.x
	Min	xx	xx	xx	xx
	Max	xx	xx	xx	xx
	n	nn	nn	nn	nn
VISIT 6	Mean	xx.x	xx.x	xx.x	xx.x
MIV-711-201	SD	xx.xx	xx.xx	xx.xx	xx.xx
WEEK 14	Median	xx.x	xx.x	xx.x	xx.x
	Min	xx	xx	xx	xx
	Max	xx	xx	xx	xx
	n	nn	nn	nn	nn
VISIT 8	Mean	xx.x	xx.x	xx.x	xx.x
MIV-711-201	SD	xx.xx	xx.xx	xx.xx	xx.xx
WEEK 26	Median	xx.x	xx.x	xx.x	xx.x
	Min	xx	xx	xx	xx
	Max	xx	xx	xx	xx

PAREXEL International SAP Amendment Shells

Medivir
Protocol: MIV-711-202

Final 1.0
16 January 2018

Medivir
Protocol Number: MIV-711-202

Page X of Y

Table 14.2.3.1
NRS Scores Observed and Change from Baseline Summary
ITT Population

Parameter = How Active the target knee arthritis has been

		Group A N = x		Group B N = x	
		Observed	Change	Observed	Change
Visit	Statistic	N = x	N = x	N = x	N = x
	n	nn	nn	nn	nn
VISIT 4	Mean	xx.x	xx.x	xx.x	xx.x
MIV-711-202	SD	xx.xx	xx.xx	xx.xx	xx.xx
	Median	xx.x	xx.x	xx.x	xx.x
WEEK 40	Min	xx	xx	xx	xx
	Max	xx	xx	xx	xx
	n	nn	nn	nn	nn
VISIT 5	Mean	xx.x	xx.x	xx.x	xx.x
MIV-711-202	SD	xx.xx	xx.xx	xx.xx	xx.xx
	Median	xx.x	xx.x	xx.x	xx.x
WEEK 52	Min	xx	xx	xx	xx
	Max	xx	xx	xx	xx

Baseline is defined as: Visit 2 in the MIV-711-201 study for Group A and Group B

Programming note: table will include summaries for following other NRS scores:

- Amount of pain severity in the target knee last week (SDTM: Overall pain severity in target knee)
- Global Assessment Score: How active has the target knee arthritis has been in the past week (SDTM: How active was target knee arthritis)
- Satisfaction with target knee function (SDTM:How satisfied are you with target knee function)
- Worst pain severity in target knee (SDTM: Worst pain severity in target knee)
- Overall pain severity in other knee (SDTM: Overall pain severity in other knee)

PAREXEL International SAP Amendment Shells

Medivir
Protocol: MIV-711-202

Final 1.0
16 January 2018

Medivir
Protocol Number: MIV-711-202

Page X of Y

Table 14.2.3.2
Statistical Analysis of NRS Scores, ITT Population

Endpoint	Group	Week	N	Estimated Mean Level		Estimated Change from Visit 2 Study MIV-711-201	
				LS Mean	95% CI	LS Mean Difference from V2 MIV-711-201	95% CI
				xxxxx	A	1 (V2: 201)	nn
		8 (V5: 201)	nn	xx.xx	(x.xx, x.xx)	xx.xx	(x.xx, x.xx)
		14 (V6: 201)	nn	xx.xx	(x.xx, x.xx)	xx.xx	(x.xx, x.xx)
		26 (V8: 201)	nn	xx.xx	(x.xx, x.xx)	xx.xx	(x.xx, x.xx)

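### Group B is selected on the NRS rise from 201 Visit 2 to Visit 8, and both readings then serve as its pain reference, so neither change can be read as a treatment effect

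*Protocol*

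**What the plan says.** Entry to Group B (Protocol 5.1, criterion 1) needs placebo treatment in 201 and a rise of at least 2 in average target-knee NRS, taken as "increase from Baseline (Visit 2 of Study MIV-711-201) to Visit 8 of Study MIV-711-201".

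**Visit 8 as reference.** Protocol 9.5.3.1 says: "For Study Population B, changes from Baseline will be assessed using the Visit 8 data from Study MIV-711-201". SAP section 8 repeats it: "Visit 8 in study MIV-711-201 for study group B". The footnotes of Listings 16.2.6.2 (NRS), 16.2.6.14 (WOMAC) and 16.2.6.22 (e-diary) agree. Biomarkers alone differ: "The exception is for the biomarkers in study group B, where the baseline visit is defined as visit 2 in the present study".

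**201 Visit 2 as reference.** For the mixed model, SAP 8.1.1 says: "The mean level and the change from visit 2 in study MIV-711-201 will be estimated for each population*visit combination". SAP 8.3.1.1 carries this to pain: "The statistical analysis of NRS Pain data will be performed using the same statistical analysis as for the Imorphics MRI". SAP 8.3.3.1 and 8.3.7.2 do the same for WOMAC and the e-diary. The NRS, WOMAC and e-diary change tables in SAP section 14 carry the footnote "Baseline is defined as: Visit 2 in the MIV-711-201 study for Group A and Group B".

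**Measurement.** In 202 these questionnaires are completed only at Visits 4 and 5, on drug (Protocol 7.9). Group B has no control, and Protocol 9.1.3 rules out comparison with Group A. Neither document mentions regression to the mean.

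**The concern.** Choosing patients because the difference between two noisy readings is large distorts both readings. The later one tends to be too high for these patients and the first too low. A change from Visit 8 then contains a fall that would occur without drug, and a change from 201 Visit 2 contains the rise used to select them.

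The plan reports both without a caveat, and the table footnotes contradict SAP section 8 on which is the baseline. The shells do not settle it. Table 14.2.3.1 fills Group B's Change cells at the visit its footnote calls baseline. Table 14.2.6.3 leaves Group B's Change blank at Visit 8 under a footnote naming Visit 2.

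Protocol 2.4 says Group B may inform patient selection in later OA trials, and NRS, WOMAC and e-diary pain have planned model tables with confidence intervals. An uncontrolled fall of a point from Visit 8 could be taken as benefit when selection can produce it.

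**Working it through.** The plan states no expected Group B change, so there is no figure to reproduce.

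**Inputs from the documents:** entry cut of 2 points; 0-10 scale; readings at 201 weeks 0, 8, 14 and 26 (SAP 4.1) and 202 Visit 5, placed at about week 53.4 after screening.

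**Assumed inputs:** mean 4.5-6.5, SD s = 1.5-2.5, correlation over 26 weeks ρ = 0.3-0.7, stable placebo mean, no drug effect, no open-label response.

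**Formulas.** Let D = Visit 8 minus 201 Visit 2.
- SD(D) = s√(2(1-ρ)), and with a stable mean E[D | D ≥ 2] = SD(D) × φ(t)/(1-Φ(t)), where t = 2/SD(D).
- The expected departure of a reading at week w from the population mean is E[D | D ≥ 2] × (r(w,26) - r(w,0)) / (2(1-ρ)). It equals +½ of the selected rise at Visit 8 and -½ at 201 Visit 2.

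**Example, s = 2, ρ = 0.5, continuous scale.** SD(D) = 2, t = 1, and the selected rise is 2 × 0.2420/0.1587 = 3.05.
- Equal correlation: Visit 5 returns to the population mean. Change from Visit 8 is -3.05/2 = -1.53; from 201 Visit 2 it is +1.53.
- AR(1): r(53.4,26) = 0.5^(27.4/26) = 0.482 and r(53.4,0) = 0.5^(53.4/26) = 0.241, so the Visit 5 factor is 0.241. Change from Visit 8 is 3.05 × (0.241 - 0.5) = -0.79; from 201 Visit 2 it is 3.05 × 0.741 = +2.26.
- Permanent worsening: 0 from Visit 8 and the whole rise from 201 Visit 2.

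**Whole-number scale clipped to 0-10, simulated over the assumed grid:**

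| Pattern | Visit 5 minus Visit 8 | Visit 5 minus 201 Visit 2 |
|---|---|---|
| Equal correlation | about -1.1 to -1.7 | about +1.1 to +1.8 |
| AR(1) | about -0.4 to -1.3 | about +1.6 to +2.3 |
| Permanent | 0 | whole rise, +2.3 to +3.0 |

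A second set of runs (means 5 and 6) agrees. At mean 6, SD 2, ρ = 0.5 it gives -1.33 and +1.37 under equal correlation.

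**Placebo mean improvement, equal correlation:**
- 1 point, held: -1.55 to -2.06 from Visit 8; +0.53 to +1.11 from 201 Visit 2.
- 1.5 points, held: -1.78 to -2.27 and +0.29 to +0.82.

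Without an open-label response, no case run reversed the direction on either reference.

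**Week 8/14 reference.** Visit 5 minus the mean of 201 weeks 8 and 14 has no-drug expectation 0 under equal correlation, +0.52 to +1.09 under AR(1), +0.61 to +1.22 if worsening partly lasts, and +1.29 to +1.66 if permanent. In the AR(1) example, the week 8 factor is 0.619 - 0.808 = -0.189 and the week 14 factor is 0.726 - 0.689 = +0.037, mean -0.076. The contrast is 3.05 × (0.241 + 0.076) = +0.97 on the continuous scale.

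**The case against.** The governing text is clear: Protocol 9.5.3.1, SAP section 8 and the listings all name Visit 8, and the footnote looks like a copied line. The model change from 201 Visit 2 is deliberate and labelled: it describes the whole two-study period, and Table 14.2.3.2 prints Group B's mean at every visit, so the selected rise is visible at week 26. Group B efficacy is exploratory, uncontrolled and unpowered. All of this stands. It argues for keeping the labelled model change, not for leaving the footnotes contradictory or the selection effect unstated.

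A reader might infer four stronger things that the documents do not support.
- **That +1.1 is a floor for the change from 201 Visit 2.** It needs a stable placebo mean, on which the documents are silent.
- **That the plan will produce changes of opposite sign.** This is an expectation without drug effect or open-label response, and under permanent worsening the Visit 8 change is zero.
- **That the artefact would usually exceed the confidence interval.** This depends on the assumed grid and on all 80 placebo patients (240/3) being available for selection. With half the resulting number of Group B patients, it did so in none of the AR(1) cases.
- **That the protocol and SAP disagree on Group B's e-diary baseline.** The protocol sentence is in 7.4.1, headed for Population A, where 201 Visit 2 is right. SAP 4.5.3 names Visit 8 without distinguishing groups, so the mismatch is for Group A.

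**Conclusion.** The point holds. Both selection readings become Group B's pain reference, and the table footnotes contradict SAP section 8. Under the stated assumptions, selection alone gives about 0 to -1.7 points from Visit 8 and about +1.1 to +2.3 from 201 Visit 2, or the whole real rise if worsening is permanent. With a placebo improvement of 1 to 1.5 points, the second figure can be as small as about +0.5 to +0.3 and the first as deep as about -2.1 to -2.3. The documentary conflict is certain; the sizes rest on assumed mean, SD, correlation and correlation pattern. Neither change is a treatment effect. The consequence is confined to interpreting exploratory Group B efficacy.

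**What to change.** 1. For Group B's patient-reported change-from-baseline summaries, use 201 Visit 8 as in Protocol 9.5.3.1 and SAP section 8. Correct the Group B footnotes and the blank or filled Change cells in the NRS, WOMAC and e-diary tables. Make the e-diary baseline in SAP 4.5.3 group-specific: 201 Visit 2 for Group A, 201 Visit 8 for Group B. Delete the 201 week 8 row of Table 14.2.6.2, since the 201 schedule has no e-diary then.
2. Keep the labelled model change from 201 Visit 2 as a whole-period description. Add for Group B, from the same model, Visit 5 minus Visit 8 and, for NRS and WOMAC, Visit 5 minus the mean of 201 weeks 8 and 14 (week 14 only for the e-diary). The pairwise difference already comes from "LSMEAN group*visit / diff CL ALPHA=0.1"; the averaged contrast is one further estimate.
3. State beside these outputs that change from Visit 8 includes regression to the mean; that change from 201 Visit 2 includes the selected rise; that the week 8/14 contrast is unbiased only if visits are equally correlated and otherwise leans towards worsening (about +0.5 to +1.1 under AR(1), up to about +1.7 if worsening is permanent); that open-label response can affect all three; and that none is a treatment effect or a decision rule.
4. Limit the programming note under Table 14.2.3.2, on what a successful study should show, to Group A.

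Items 1, 3 and 4 are text and shell edits. Item 2 uses data already in the model. The price is that Group B's apparent symptom improvement will look smaller. An untreated questionnaire before the first 202 dose is no longer possible at SAP stage and is not part of this fix.
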